We propose a randomized crossover study to compare active versus sham RIC combined with one bout of isometric hand exercise. Participants will be randomly assigned the order of the two experimental sessions: active or sham RIC. The isometric hand exercise will be performed in both sessions. The washout period between the two experimental sessions will be two to three weeks to prevent any carry-over effects. Figure 1 outlines the experimental protocol. Each session will consist of a pre-test measurement (baseline), active/sham RIC, post-RIC measurement, an isometric hand exercise and a post-exercise measurement. The total time in each session is around 3 hours including preparation. At the beginning and end of active/sham RIC, blood samples will be collected to measure changes in inflammatory mediators.

[figure not shown]

Figure 1. The experimental protocol.

Participants with chronic cSCI (n=8, ASIA Impairment Scale (AIS) A-D) and age-matched (within ± 5 years) able-bodied controls (n=8) will be recruited. Participants with cSCI must have at least partial ability to make volitional finger opposition movements (thumb and index finger) in at least one hand. Participants will be excluded if they have concurrent serious medical illness, traumatic brain injury, cardiovascular or pulmonary complications, seizure history, deep vein thrombosis, or any other issues that would increase risk of magnetic or electrical stimulation required for outcome measure assessment. We will also document medications that participants are currently using for systemic inflammation, spasticity, anxiety, or depression, which could affect nervous system excitability. One screening session will be conducted to confirm eligibility and determine the target arm in each participant. The arm with consistent responses on abductor pollicis brevis muscle (APB) induced by magnetic or electrical stimulation will be the target arm. Transcranial magnetic stimulation (TMS) will be performed to determine each subject's optimal scalp location for hand motor cortex stimulation, and to determine resting motor threshold for the APB muscle. Participants will be withdrawn if TMS-induced motor evoked potentials (MEPs) are unable to be detected at the APB muscles on either hand at stimulus intensity below 90% of maximal stimulator output. More details regarding inclusion and exclusion criteria are listed in the human subject section.

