Participants with chronic cSCI (n=8, ASIA Impairment Scale (AIS) A-D) and age-matched (within ± 5 years) able-bodied controls (n=8) will be recruited. Participants with cSCI must have at least partial ability to make volitional finger opposition movements (thumb and index finger) in at least one hand. Participants will be excluded if they have concurrent serious medical illness, traumatic brain injury, cardiovascular or pulmonary complications, seizure history, deep vein thrombosis, or any other issues that would increase risk of magnetic or electrical stimulation required for outcome measure assessment. We will also document medications that participants are currently using for systemic inflammation, spasticity, anxiety, or depression, which could affect nervous system excitability. One screening session will be conducted to confirm eligibility and determine the target arm in each participant. The arm with consistent responses on abductor pollicis brevis muscle (APB) induced by magnetic or electrical stimulation will be the target arm. Transcranial magnetic stimulation (TMS) will be performed to determine each subject's optimal scalp location for hand motor cortex stimulation, and to determine resting motor threshold for the APB muscle. Participants will be withdrawn if TMS-induced motor evoked potentials (MEPs) are unable to be detected at the APB muscles on either hand at stimulus intensity below 90% of maximal stimulator output. More details regarding inclusion and exclusion criteria are listed in the human subject section.

The RIC protocol involves 5 cycles of 5-min inflation and 5-min deflation on the non-target arm. RIC will be achieved via blood pressure cuff inflation to 200 mmHg for active RIC³⁷⁻⁴⁰ and 10 mmHg below the subjects' diastolic blood pressure for sham conditioning. This method replicates RIC as it has been applied in many other studies^{23,38,41}.

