Hypothesis 3A: There will be no difference in HR, BP and SaO₂ (pulse oximeter on the finger of the target arm) responses among baseline, inflation phase, deflation phase and post-RIC during active and sham RIC in persons with SCI and able-bodied controls.

Although RIC has been shown to be safe in the healthy able-bodied population as well as in individuals with heart disease and critically ill patients with subarachnoid hemorrhage^{39,40,59}, there are no data describing the safety of RIC in persons with SCI. The SCI population, particularly those with cSCI, have widespread sensory impairment, including a limited ability to feel pain/discomfort. In addition, damage to the ANS after cSCI contributes to cardiovascular dysregulation and may alter hemodynamic responses to RIC. Several studies⁶⁰⁻⁶³ have reported stable HR and BP responses before and after RIC not just in healthy participants but also in participants with heart diseases or vascular stenosis. The BP responses even remained unchanged during the whole course of RIC in able-bodied participants and in participants with stable angina pectoris^{60,62}. However, the sympathetic hypoactivity after cSCI might result in altered or delayed hemodynamic responses, possibly leading to fluctuation of HR and BP. Therefore, we will real-time record HR, BP and SaO_2 on the contralateral arm and document the pain scale and any adverse effects during RIC.

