Method: During the 50-minute active and sham RIC (5 cycles of 5 min inflation plus 5 min deflation), beat-to-beat HR, RR and SaO_2 will be monitored in real-time and digital signals will be stored on a computer hard-drive for subsequent analysis. **Electrocardiogram** - A 3-lead ECG (UFI: model RESP 1, Morro Bay CA) will be used to measure beat-to-beat HR during testing. Electrodes will be placed at the right and left clavicle and in the V-5 position; data will be recorded from V-5. **Finger Arteriolar Blood Pressure** - Beat-to-beat BP will be continuously monitored from the left middle or ring finger using photoplethysmography (FMS: Finometer, Pro; Amsterdam, Netherlands). HR and finger arteriolar BP will be viewed in real time on a computer screen and will be stored for offline analysis using customized programs written with LabView graphical software. **Brachial Blood Pressure and Oxygen Saturation (SaO_2)** - Brachial BP and SaO_2 will be measured by a trained technician using a standard adult BP cuff (GE Healthcare Information Technologies, Milwaukee, WI) with a finger pulse oximeter at 1 minute intervals during administration of the sham and RIC conditions. The peak HR, BP and the minimal SaO_2 in baseline, inflation phase, deflation phase and post-RIC will be reported for statistical analysis.

Statistical analysis: Changes from baseline in HR, BP and SaO_2 will be compared following RIC and Sham conditions in the cSCI and Able-bodied groups separately using a 2 (RIC, Sham) by 4 (baseline, inflation, deflation and post-RIC) repeated measures ANOVA to measure the hemodynamic responses for the within subject variability, and to determine main and interaction effects with Tukey post-hoc analyses. If the data is not normally distributed and the assumptions of the ANOVA are not met, Wilcoxon signed rank tests will be used instead. Post hoc pairwise comparisons will be performed using the Bonferroni adjustment, if there are any main or interaction effects within the two independent variables. The pain scale will be also compare with the same ANOVA model.

Project timeline

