The IRB protocol will be submitted within the first month of funding notification. We expect to obtain the full approval within two months. We estimate one participant with SCI and one able-bodied control every two months, so the total enrollment period would be completed in about 16 months. We will begin the data analysis after the first two or three participants and continue to examine subject responses and modify the protocol if and when necessary. During the final quarter of the funding period, we will prepare a manuscript to disseminate the findings.

[figure not shown]

Figure 3. The equipment configuration of testing HR variability, respiratory rate and blood pressure changes during RIC/Sha conditioning.

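### Aim 3 analyses HR and BP only as per-phase peaks, so a brief fall cannot appear in the planned test; the finger-BP site is also contradictory, and the hypothesis of no difference has no stated criterion

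*Combined protocol and SAP*

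**What the plan says.** **Sensor site.** The Approach (Overview) puts the cuff opposite the test arm: "The RIC protocol involves 5 cycles of 5-min inflation and 5-min deflation on the non-target arm". The test arm is chosen by response at screening: "The arm with consistent responses on abductor pollicis brevis muscle (APB) induced by magnetic or electrical stimulation will be the target arm". The rationale under Hypothesis 3A says "we will real-time record HR, BP and SaO_2 on the contralateral arm", and the hypothesis itself puts the oximeter on the target arm. The Aim 3 Method says "Beat-to-beat BP will be continuously monitored from the left middle or ring finger using photoplethysmography", with no exception. It adds a second BP source at one-minute intervals, without naming the arm: "Brachial BP and SaO_2 will be measured by a trained technician using a standard adult BP cuff". It does not say which BP is analysed. HR comes from a 3-lead ECG.

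**Analysed summaries.** The Aim 3 Method sends to analysis the peak of HR and BP and the minimum of SaO2 in each of four phases (baseline, inflation, deflation, post-RIC). HR and finger BP are displayed live and stored. The rationale adds that pain and adverse effects are documented.

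**Inference.** Hypothesis 3A predicts no difference across phases in either condition. The Statistical analysis paragraph gives a 2 (active, sham) by 4 (phase) repeated-measures ANOVA, with Wilcoxon tests as fallback, run separately in the 8 participants with cervical injury and the 8 controls. It states no margin and no interval estimate.

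**The concern.** The rationale says that no safety data exist for RIC in spinal cord injury and that reduced sympathetic activity may make HR and BP fluctuate. Fluctuation includes falls. A maximum records rises, and it registers a fall only if the fall lasts through the phase. The planned result would therefore be silent on one of the two directions that the authors have in mind.

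The other two parts affect how that result can be read. If the finger sensor lies below the RIC cuff, its trace could be lost in the active session but not in the sham session, so the loss would differ between the conditions being compared. And a non-significant ANOVA in 8 people could be taken as support for Hypothesis 3A when moderate differences would often be missed.

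**Working it through.** The plan gives no SD, margin or power for Aim 3, so there is no figure of its own to reproduce.

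**1. Sensor site, passages side by side.**
- Target arm left: the cuff is on the right. A left finger sensor is contralateral, and the texts agree.
- Target arm right: the cuff is on the left. The Method puts the finger sensor on the left, below the cuff; the rationale puts BP recording on the right. Both cannot hold.

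Pressures differ by condition. In the active session, "RIC will be achieved via blood pressure cuff inflation to 200 mmHg for active RIC"; in the other, the cuff is set 10 mmHg below "diastolic blood pressure for sham conditioning". If systolic BP is under 200 mmHg (assumed), the finger trace of a left-cuffed participant could be interrupted for up to 5 x 5 = 25 of the 50 minutes in the active session and not in sham. One-minute brachial readings would continue if taken on the contralateral arm. The number of left-cuffed participants is unknown.

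**2. Peak versus lowest value.** Illustration for one phase (assumed mean 110, SD 6 mmHg, 350 autocorrelated beats, one 35-beat fall of 30 mmHg): the mean peak is 125.5 without the fall and 125.2 with it, and the peak is identical in 91% of runs. The mean minimum goes from 94.6 to 71.4.

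Trial-level simulation, with all SDs assumed: 8 participants, 2 conditions, four phases of 5/25/25/5 one-minute readings (baseline and post-RIC lengths assumed). Reading SD is 4 or 8 mmHg, subject SD 10, session SD 5, and session-by-phase SD 0, 5 or 8. The fall is 20 mmHg during active inflation, for one minute unless sustained. The test is the condition-by-phase interaction at p<0.05. Ranges are over the six settings, with 4,000 trials each.

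| Pattern | Peak | Lowest value over all cycles |
|---|---|---|
| No fall | 5% | 5-6% |
| All 8 fall, every cycle | 5-6% | 47-100% |
| All 8 fall, one cycle | 5% | 12-100% |
| 2 of 8 fall, every cycle | 5% | 6-11% |
| 2 of 8 fall, one cycle | 5% | 5-10% |
| All 8, fall sustained through inflation | 82-100% | not needed |

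The wide range in the third row depends on noise. With reading SD 8 it is about 12-32%; 100% occurs only with reading SD 4 and no session-by-phase variation. In a participant who falls in one cycle, the lowest inflation value is on average 6-12 mmHg below sham, while the peak moves by 0.3 mmHg or less. Averaging the five cycle minima, instead of taking the lowest, cuts detection in the third row to 6-50%. HR was not simulated; the logic of a maximum is the same.

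**3. Inference with n=8, two-sided 5% (assumed).**
- Paired contrast, noncentral t with 7 df and noncentrality d x sqrt(8): power is 23%, 50% and 68% at d = 0.5, 0.8 and 1.0 SD of the paired difference.
- Planned interaction, F(3,21), sphericity, effect in one phase, d in SDs of the active-minus-sham change from baseline: noncentrality = 8 x 0.75 x 2d² = 12d², that is 3.0, 7.7 and 12.0. Power is 23%, 55% and 76%.
- 95% CI half-width: t(0.975, 7)/sqrt(8) = 2.365/2.828 = 0.84 SD. If the SD of differences is 10 or 15 mmHg (assumed), this is 8.4 or 12.5 mmHg.

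**The case against.** **The site conflict is narrow.** The rationale and the hypothesis both point to the arm opposite the cuff, and the word left may be a generic equipment description. The relevant drawing ("Figure 3. The equipment configuration of testing HR variability, respiratory rate and blood pressure changes during RIC/Sha conditioning") is not shown and may settle the matter. A trace lost on inflation would be seen live, and brachial BP may cover the gap. This stands in large part. A reader might infer that half of the finger-BP data will be lost in active sessions; the documents do not support that. What remains is two written instructions that cannot both be followed in a right-target participant, and an unnamed BP source.

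**The peak problem does not blind the study.** Live viewing, stored signals and adverse-effect documentation mean that a fall could be noticed and reported. This stands: it would be wrong to infer that Aim 3 cannot show hypotension or bradycardia at all, or that peaks miss every fall. The gap is confined to brief falls in the planned statistical result. It is also fair that a group test on minima gains little when only 2 of 8 fall, and that the simulated percentages depend on assumed SDs.

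**Non-significance is nowhere declared to be proof.** The plan says only that changes will be compared. The study is labelled preliminary, Aim 3 is not the primary outcome, and omitting CIs from a short plan does not rule them out. This also stands, so the inference point is minor. But the plan offers no other criterion for a hypothesis worded as no difference.

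**Conclusion.** The point holds in limited form. The main part is the choice of summary: with peaks only, a brief fall in HR or BP cannot register in the planned test, and simulated detection for BP stays at the 5% chance level under every brief-fall pattern tried. This follows from what a maximum measures; only the detection figures for the lowest value rest on assumed SDs. If peak is read as applying to HR alone, no BP summary is defined at all, which also needs correcting.

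The sensor-site conflict is certain as text, but its effect on the data is unknown. It depends on how many participants are cuffed on the left, on which instruction is followed, and on a figure that is not shown. ECG-derived HR is unaffected.

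The inference part is minor. A reader might conclude that the investigators will treat p>0.05 as showing no difference; the documents do not say so. With 8 per group, though, a true difference of 0.5 to 0.8 SD would be missed in a paired contrast about 77% to 50% of the time, so the plan should exclude that reading. A group size of 8 is not itself a fault in a preliminary study.

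**What to change.** 1. **Site and source.** Reconcile the rationale and the Method of Aim 3 on the finger-sensor site, and name which BP (finger or brachial) is analysed.
2. **Summaries.** From the stored traces, list each participant's lowest and highest HR and BP per phase and condition; this is the main remedy for isolated falls. Also summarise the minimum and mean per phase for active versus sham, taking the lowest value over all five cycles. State an artefact filter or short averaging window. Compare phases on extremes only over windows of equal length, because extremes over unequal windows differ with no true change.
3. **Inference.** Report active-minus-sham differences with 95% CIs per phase and group, and add: *A non-significant result will not be read as evidence of no difference.* An equivalence margin is optional.

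**Cost.** Wording, a few summaries and one listing from HR and finger-BP signals already stored; no new visit. Whether equal windows are possible depends on the baseline and post-RIC recording lengths, which the plan does not give. Minima are sensitive to artefact, yet longer averaging dilutes brief falls: a 20-second fall of 20 mmHg becomes 20 x 20/60 = 6.7 mmHg in a one-minute mean. A group test on minima stays weak (about 5-11%) if only 2 of 8 fall, and the CIs will be wide. If the finger sensor and brachial cuff share an arm, each brachial reading briefly interrupts the finger trace, in active and sham alike.

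### Aim 3 compares peak HR/BP and minimum SaO2 across phases without fixing equal windows, so the phase comparison in Hypothesis 3A can differ from window length alone

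*Combined protocol and SAP*

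**What the plan says.** The Aim 3 Method describes the recording period as "During the 50-minute active and sham RIC (5 cycles of 5 min inflation plus 5 min deflation", with the same timing in both sessions. Brachial BP and SaO2 are read "at 1 minute intervals during administration of the sham and RIC conditions". HR comes beat by beat from the ECG, and for finger pressure "Beat-to-beat BP will be continuously monitored from the left middle or ring finger".

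The summary measure is an extreme value per phase: "The peak HR, BP and the minimal SaO_2 in baseline, inflation phase, deflation phase and post-RIC will be reported for statistical analysis". The Aim 3 Statistical analysis then applies, separately in each group, a "2 (RIC, Sham) by 4 (baseline, inflation, deflation and post-RIC) repeated measures ANOVA", looking at main and interaction effects. Any such effect opens pairwise post hoc comparisons.

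Hypothesis 3A expects no difference in "responses among baseline, inflation phase, deflation phase and post-RIC during active and sham RIC in persons with SCI and able-bodied controls". The phase comparison is therefore part of what is tested.

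The text does not state:

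- how long the baseline and post-RIC haemodynamic recordings last;
- how many readings they contain;
- whether a phase peak is the single highest value over all five cycles or a value taken within each 5-minute period and then combined.

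**The concern.** The expected maximum of a fluctuating signal rises with the length of the window searched, and the expected minimum falls. If one phase is searched for 25 minutes and another for 5, their peaks differ on average even when the signal is identical. The plan compares extremes across four phases and fixes no common window.

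At stake is the reading of Hypothesis 3A. A false phase effect would contradict the hypothesis and open pairwise comparisons, which could show BP and HR higher and SaO2 lower during conditioning than at baseline. With windows mismatched the other way, a real rise could be masked. The Aim 3 rationale says there are no data on the safety of RIC in people with SCI, so these within-session changes are likely to be read as safety evidence.

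**Working it through.** **Inputs from the documents**

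- Cycle timing (Aim 3 Method): inflation 5 × 5 = 25 min; deflation 5 × 5 = 25 min; total 25 + 25 = 50 min. This reproduces the stated 50 minutes.
- One reading per minute for brachial BP and SaO2: 25 readings per phase if the cycles are pooled.
- 8 participants per group, two sessions each, groups analysed separately.

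**Assumptions, because the documents give no figures**

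- Baseline and post-RIC windows equal to each other, at 5, 10, 15 or 25 minutes.
- Normal one-minute readings with within-person SD 1 and no true change.
- Minute-to-minute autocorrelation 0, 0.5 or 0.8.
- Two-sided 5% level, ANOVA without sphericity correction, 4,000 simulated trials per setting.

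**Step 1. Expected peak by window length.** Let E(m) be the expected maximum of m consecutive readings, in within-person SDs.

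| Autocorrelation | E(5) | E(10) | E(15) | E(25) |
|---|---|---|---|---|
| 0 | 1.16 | 1.54 | 1.74 | 1.97 |
| 0.8 | 0.66 | 1.03 | 1.25 | 1.54 |

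**Step 2. Bias if peaks are pooled over cycles:** E(25) − E(m).

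- Autocorrelation 0: 1.97 − 1.16 = 0.81; 1.97 − 1.54 = 0.43; 1.97 − 1.74 = 0.23; and 0 at 25 minutes.
- Autocorrelation 0.8: 1.54 − 0.66 = 0.88; 1.54 − 1.03 = 0.51; 1.54 − 1.25 = 0.29; and 0 at 25 minutes.

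This treats the 25 inflation minutes as one block. In the real alternating layout they are spread over 50 minutes. The bias at autocorrelation 0 to 0.8 is then 0.80–1.01 SD against 5 minutes, 0.43–0.64 against 10, 0.23–0.42 against 15 and 0.00–0.13 against 25.

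**Step 3. Bias if peaks are taken per 5-minute cycle and averaged:** E(5) − E(m).

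- Autocorrelation 0: 0 at 5 minutes; 1.16 − 1.54 = −0.38; 1.16 − 1.74 = −0.58; 1.16 − 1.97 = −0.81.
- Autocorrelation 0.8: 0; 0.66 − 1.03 = −0.37; 0.66 − 1.25 = −0.59; 0.66 − 1.54 = −0.88.

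This reading therefore gives a false fall in the peak unless baseline is also 5 minutes.

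**Step 4. False-positive rates with pooled peaks, alternating layout, n = 8** (range over the three autocorrelations)

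| Baseline and post-RIC length (assumed) | Phase main effect | Inflation vs baseline, active session | RIC-by-phase interaction | Active vs sham difference in change |
|---|---|---|---|---|
| 5 min | 98–99% | 62–65% | 5.1–6.9% | 4.6% |
| 10 min | 66–76% | 27–32% | 5.0–6.2% | 4.8–5.0% |
| 15 min | 23–43% | 12–18% | 4.8–5.2% | 4.3–4.9% |
| 25 min | 5–10% | 5–6% | 4.7–5.2% | 4.5–4.8% |

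The 9.8% phase rate at 25 minutes and autocorrelation 0.8 goes with the 0.13 SD residual in Step 2. Readings scattered over 50 minutes resemble one another less than 25 consecutive ones do.

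**Step 5. After the change.** With the peak taken per 5-minute window, averaged over five cycles and set against 5-minute baseline and post-RIC windows, false-positive rates are 6.6–7.7% for phase, 6.8–7.5% for the interaction and 5.0–5.2% for inflation versus baseline. The small excess in the two F tests is plausibly due to unequal variances: an average of five peaks varies less than a single peak.

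Under this symmetric model the minimum mirrors the maximum. SaO2 is bounded above, so the size would differ for it, but not the direction.

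**The case against.** The strongest reply is that the text does not say the baseline is shorter. A reader might infer it from the one-minute readings being scheduled during conditioning, but that phrase covers only brachial BP and SaO2. HR and finger pressure are recorded beat by beat, and the summary rule itself requires values at baseline and post-RIC, so recording there is intended. Timing may also be given in the protocol figures, which were not available here. With a 25-minute baseline the pooled bias is nil or small, and with a longer one it would reverse. Pooling over cycles is likewise not stated. All of this stands, and it is why the sizes above are conditional. It does not rescue the rule: pooled peaks need a baseline of about 25 minutes and averaged per-cycle peaks need one of 5, and the text commits to neither.

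A second tempting inference is that RIC itself, or its dose, would falsely appear to alter haemodynamics. The documents do not support that. There is no dose factor, sham has the same 50-minute structure, and the artefact is equal in both sessions. The RIC-by-phase interaction, which isolates RIC, is not materially affected. But Hypothesis 3A also covers differences among phases within each session, and a phase main effect alone triggers the pairwise tests.

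Finally, averaging cycle peaks dilutes one large excursion, which matters for a measure taken as a safety precaution. That is a fair cost, and the fix allows for it.

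**Conclusion.** The concern holds in a conditional form. The plan compares extremes across phases without matching windows, so the phase main effect and the within-session phase comparisons are biased unless the lengths happen to agree. Pooled peaks against a 5-minute baseline give about 0.8–1.0 within-person SD of spurious rise and a near-certain false phase effect; at 15 minutes the false-positive rate is 23–43%, and at 25 minutes it is close to nominal. Averaged per-cycle peaks against 10 to 25 minutes give a spurious fall of about 0.4 to 0.9 SD. The active-versus-sham contrast is sound under every window length tried.

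These sizes rest on the assumed window lengths, normal readings, autocorrelation of 0 to 0.8 and a 5% level. That the comparison depends on window length does not rest on those particular values. The point should be settled before analysis, but it does not undermine the comparison of active with sham RIC.

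**What to change.** In the Aim 3 Method, define one window length for all four phases:

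1. Record a 5-minute baseline and a 5-minute post-RIC window with the same one-minute and beat-to-beat sampling as during conditioning.
2. Take the peak HR and BP and the minimum SaO2 within each 5-minute inflation and each 5-minute deflation, and average the five values per phase for the ANOVA.
3. State that conclusions about RIC itself rest on the RIC-by-phase interaction.
4. Report the overall extreme in each phase and the values for cycles 1 to 5 descriptively, so that a single large excursion or a build-up over cycles stays visible.

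The cost is a few sentences, a change to the offline program and at most about 10 minutes (5 + 5) of extra recording per session with equipment already in use. Signal storage is described explicitly only for the 50-minute conditioning period, so the text should extend it to the two added windows.
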